# 11.2. Appendix 2: Study Phases and Treatment Emergent Adverse Events

# 11.2.1. Study Phases

Assessments and events will be classified according to the time of occurrence relative to study treatment start date(/time) and stop date(/time).

Study Phase	Definition
Pre-Treatment	Date and Time ≤ Study Treatment Start Date and Time
On-Treatment	Study Treatment Start Date and Time < Date and Time ≤ Study Treatment Stop Date and Time + 5 days
Post-Treatment	Date and Time > Study Treatment Stop Date and Time + 5 days

#### 11.2.1.1. Study Phases for Concomitant Medication

Study Phase	Definition
Prior	If medication end date is not missing and is before Day -4
Concomitant	Any medication that is not a prior

#### NOTES:

 Please refer to Appendix 5: Reporting Standards for Missing Data for handling of missing and partial dates for concomitant medication. Use the rules in this table if concomitant medication date is completely missing.

# 11.2.2. Treatment Emergent Flag for Adverse Events

Flag	Definition
Treatment Emergent	• If AE onset date and time is on or after treatment start date and time & on or before treatment stop date and time + 5 days.
	
 
Study Treatment Start Date and Time ≤ AE Start Date and Time ≤ Study Treatment Stop Date and Time + 5 days.
 

	
 
If the AE onset date is completely missing, the AE is considered as treatment emergent.
 

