#### 2.3. Study Design

 The "Washout" period of this study should be called "Follow Up" as there is only one treatment period. See 208135 Protocol Clarification dated 10-June-2019

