# 5. CONSIDERATIONS FOR DATA ANALYSES AND DATA HANDLING CONVENTIONS

# 5.1. Study Treatment & Sub-group Display Descriptors

Treatment Group Descriptions					
Data Displays for Reporting					
Description Code Order in TI					
Portia (0.03 mg EE/0.15 mg LNG) QD on Days -3 to -1	Run-in Portia	1			
Portia (0.03 mg EE/0.15 mg LNG) QD on Days 1 to 10	Treatment A	2			
Portia (0.03 mg EE/0.15 mg LNG) QD coadministered with GSK3640254 200 mg on Days 11 to 21	Treatment B	3			

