#### **Period Day**

- Calculated as the number of days from First Dose Date for the respective period:
  - Assessment Date = Missing
    - → Period Day = Missing
  - Assessment Date < Dose Date on Day -3

    - → Period Day = Assessment Date Dose Date on Day -3
  - Dose Day on Day -3 <= Assessment Date < Dose Date on Day 1

    - → Period Day = Assessment Date Dose Date on Day -3 + 1
  - Dose Date on Day 1 <= Assessment Date < First Dose Date on Day 11

    - → Period Day = Assessment Date Dose Date on Day 1 + 1
  - Assessment Date >= First Dose Date on Day 11
    - → Period Day = Assessment Date First Dose Date on Day 11 + 1

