# 11.9.5. Safety Tables

Safety:	Tables				
No.	Population	IDSL / Example Shell	Title	Programming Notes	Deliverable [Priority]
Advers	e Events (AEs)				 
2.1.	Safety	AE1CP	Summary of Adverse Events by System Organ Class and Preferred Term		SAC
2.2.	Safety	AE1CP	Summary of Drug-Related Adverse Events by System Organ Class and Preferred Term		SAC
2.3.	Safety	AE3	Summary of Common (>=5%) Adverse Events by Overall Frequency		SAC
2.4.	Safety	AE15	Summary of Common (>=5%) Non-serious Adverse Events by System Organ Class and Preferred Term (Number of Subjects and Occurrences)		SAC
2.5.	Safety	AE16	Summary of Serious Adverse Events by System Organ Class and Preferred Term (Number of Subjects and Occurrences)		SAC
2.6.	Safety	AE5A	Summary of Adverse Events by System Organ Class and Preferred Term and Maximum Intensity		SAC
2.20.	Safety	AE1CP	Summary of Adverse Events of Special Interest		SAC
Labora	tory: Chemistry	/			·
2.7.	Safety	LB1	Summary of Clinical Chemistry Changes from Baseline		SAC
2.21.	Safety	LB1	Summary of Clinical Chemistry Values		SAC
2.8.	Safety	LB16	Summary of Clinical Chemistry Results by Maximum Grade Increase Post-Baseline Relative to Baseline		SAC
Labora	tory: Hematolo	gy			·
2.9.	Safety	LB1	Summary of Hematology Changes from Baseline		SAC

Safety:	Tables				
No.	Population	IDSL / Example Shell	Title	Programming Notes	Deliverable [Priority]
2.22.	Safety	LB1	Summary of Hematology Values		SAC
2.10.	Safety	LB16	Summary of Hematology Results by Maximum Grade Increase Post-Baseline Relative to Baseline		SAC
Labora	tory: Urinalysis	;			 
2.11.	Safety	UR3	Summary of Urinalysis Dipstick Results		SAC
2.12.	Safety	LB1	Summary of Urine Concentration Changes from Baseline		SAC
2.23.	Safety	LB1	Summary of Urine Concentration Values		SAC
2.13.	Safety	LB16	Summary of Urinalysis by Maximum Grade Increase Post- Baseline Relative to Baseline		SAC
ECG					
2.14.	Safety	SAFE_T1	Summary of ECG Findings		SAC
2.15.	Safety	EG2	Summary of ECG Changes from Baseline		SAC
2.24	Safety	EG2	Summary of ECG Values		SAC
2.16.	Safety	EG10	Summary of Maximum QTc Values Post-Baseline Relative to Baseline by Category		SAC
2.17.	Safety	EG11	Summary of Maximum Increase in QTc Values Post-Baseline Relative to Baseline by Category		SAC
Vital Si	gns				•
2.18.	Safety	VS1	Summary of Vital Sign Changes from Baseline		SAC
2.25.	Safety	VS1	Summary of Vital Sign Values		SAC

Safety:	Safety: Tables					

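### The adverse-event columns cover unequal time (3, 10 and probably 14 to 15 days), the SAP does not say which column takes Day 22–25 onsets, and no rate is planned

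*SAP*

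**What the plan says.** SAP section 5.1 defines the display columns: "Portia (0.03 mg EE/0.15 mg LNG) QD on Days -3 to -1" (Run-in Portia), "Portia (0.03 mg EE/0.15 mg LNG) QD on Days 1 to 10" (Treatment A) and Portia "QD coadministered with GSK3640254 200 mg on Days 11 to 21" (Treatment B). It lists no follow-up column.

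Section 11.2.2 flags an event as treatment emergent if its onset is "on or before treatment stop date and time + 5 days". Section 11.2.1 gives the on-treatment phase the same tail: "Study Treatment Start Date and Time < Date and Time ≤ Study Treatment Stop Date and Time + 5 days". Both are tied to study treatment as a whole, not to each column. That agrees with the note in section 2.3, which renames the washout as follow-up "as there is only one treatment period".

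The Time and Events table (section 11.1.1) runs to Day 25, the day of discharge and of the 96-hour sample after the Day 21 dose. The Period Day rule (section 11.4.1) opens the last period with "Assessment Date >= First Dose Date on Day 11" and gives it no end.

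Section 11.3.2 summarises categorical data as counts and percentages. Section 11.9.5 lists the event displays, beginning with Table 2.1, "Summary of Adverse Events by System Organ Class and Preferred Term", with empty programming notes. No participant-time or rate display is listed.

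**The concern.** Tolerability of the combination is a secondary objective (section 2.2). In this single-sequence study, Portia alone is the only comparator a reader has. Most readers will set column A beside column B in the overall, drug-related and special-interest tables.

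If B also collects the follow-up onsets, it is watched for about half as long again as A, and crude percentages do not show this. Some or all of an excess on B could then come from the longer window and be read as an effect of GSK3640254. If instead the follow-up onsets go elsewhere, the SAP should say where. Two programmers could fill the same table differently and both claim to follow the text.

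**Working it through.** The SAP gives no event rate, participant-time or expected count, so there is no figure of its own to reproduce. The check counts the windows and asks what they imply with no drug effect.

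**Windows**
- Run-in: Days -3 to -1 = 3 days (section 5.1).
- Treatment A: Days 1 to 10 = 10 days (section 5.1).
- Treatment B, dosing only: Days 11 to 21 = 11 days (section 5.1).
- Treatment B with follow-up: Days 11 to 25 = 11 + 4 = 15 calendar days, or 10 + 4 = 14 elapsed days from the Day 11 dose to 96 hours after the Day 21 dose (section 11.1.1). The 5-day tail does not end before Day 25.

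**Model (assumptions)**
Onset rate constant over time, no drug effect, every participant observed to Day 25, and follow-up onsets counted under B. If p is the proportion of participants with an event in the 10 days of A, then over d days:

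- expected events relative to A = d/10
- proportion with at least one event = 1 − (1 − p)^(d/10)

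| Column | d | Events vs A | p = 10% | p = 20% | p = 40% |
|---|---|---|---|---|---|
| Run-in | 3 | 0.3 | 3.1% | 6.5% | 14.2% |
| A | 10 | 1.0 | 10.0% | 20.0% | 40.0% |
| B, Days 11–21 only | 11 | 1.1 | 10.9% | 21.8% | 43.0% |
| B, to 96 hours | 14 | 1.4 | 13.7% | 26.8% | 51.1% |
| B, Days 11–25 | 15 | 1.5 | 14.6% | 28.4% | 53.5% |
| Run-in + A (not a planned column) | 13 | 1.3 | 12.8% | 25.2% | 48.5% |

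Worked case: 1 − 0.8^1.5 = 28.4% and 1 − 0.8^1.1 = 21.8%. Most of the gap between A and B comes from the follow-up days (1.1 to 1.5), not from the one extra dosing day (1.0 to 1.1). Against run-in plus A the ratio is 15/13 = 1.15.

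**How reliably would an excess appear?** With 20 participants per column (assumed, as the SAP gives no number), 15 days on B, and the columns treated as independent, simulation puts the chance that B's count exceeds A's at 0.58 for p = 10% and 0.76 for p = 40%. An excess is likely but not certain.

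**Sensitivity to a time trend.** If the onset rate instead falls from Day 1 with half-life h, let k = ln 2/h. Expected events on B (15 days) relative to A are then e^(−10k)(1 − e^(−15k))/(1 − e^(−10k)).
- h = 20 days: 0.707 × 0.405/0.293 = 0.98.
- h = 10 days: 0.500 × 0.646/0.500 = 0.65.

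So a declining rate can cancel or reverse the excess.

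**The case against.** The strongest reply is that the premise is not written in the plan. A reader might infer that follow-up is folded into Treatment B as a rule. The documents do not say so. Section 5.1 ends B at Day 21, section 11.2.2 sets a flag and assigns no column, the Period Day rule defines a day number, and section 11.3.2 says only that data follow the treatment actually received. The layout of the sponsor's standard table shell is not shown. This objection stands, but it leaves the attribution unwritten, which is itself the gap. Attaching the 5 days to each treatment would not help, because A would then run to Day 15 and overlap B.

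A reader might also infer that B must show more events by construction. That needs a roughly constant onset rate, and the SAP gives no rate. In a fixed sequence, time and treatment are confounded. This limit stands.

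A third inference is that the 5% cut-off for common events becomes easier to reach on B. Table 2.3 is by overall frequency, and nothing shows that the cut-off is applied within a column, so this is not supported.

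It is also fair that:
- the run-in is Portia alone as well, which narrows the contrast;
- 15 days assumes completion to Day 25;
- exposure is summarised and all events are listed;
- the displays are descriptive, with no formal comparison of A with B.

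These points lower the stakes. They do not put the unequal time in front of someone reading Table 2.1.

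**Conclusion.** The point holds in a limited form. The three columns cover unequal time, events are shown only as crude counts and percentages, and the SAP does not fix the column for Day 22–25 onsets. The most natural reading gives B about 14 to 15 days against 10 for A. At a roughly constant onset rate with no drug effect and full follow-up, that means about 1.4 to 1.5 times as many expected events on B: at 20% on A, about 27% to 28% on B, of which only the step to about 22% comes from dosing days. The direction is not guaranteed. The short run-in column is a feature of the design, not of the follow-up rule. The primary pharmacokinetic analysis is untouched. This is a cheap improvement to how tolerability is displayed, not a flaw in the main inference.

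**What to change.** Leave the 5-day emergent rule as it is, and make three changes to the SAP:

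1. State in section 11.2.2 that each event is assigned to the most recent treatment at onset, so that onsets after the last Treatment B dose, within the emergent window, count under B.
2. In Tables 2.1, 2.2 and 2.20, split Treatment B into onset on Days 11–21 and onset in follow-up (Day 22 onward), and keep the B total.
3. In the same tables, add participant-days observed and events per 100 participant-days for each column. This also accounts for participants who leave early.

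Compare A with B descriptively on the Days 11–21 sub-column or on the rate, with a note that neither removes a time trend in a single-sequence design.

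The cost is a few lines of SAP text and slightly wider tables. The dates needed are already used for the emergent flag.

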#### NOTES:

- If the study treatment stop date is missing, then the AE will be considered to be On-Treatment.
- Please refer to Appendix 5: Reporting Standards for Missing Data for handling of missing and partial dates for adverse events. Use the rules in this table if the adverse event onset date is completely missing.

#### 11.3. Appendix 3: Data Display Standards & Handling Conventions

#### 11.3.1. **Reporting Process**

Software								
The currently supported versions of SAS software (9.4) will be used.								
Reporting Area	Reporting Area							
HARP Server	\\us1salx00259.corpnet2.com							
HARP Compound	\gsk3640254\mid208135\final_01							
Analysis Datasets								

- Analysis datasets will be created according to CDISC standards (SDTM IG Version 3.2 & ADaM IG Version 1.1).
- For creation of ADaM datasets (ADC1/ADCM/ADAE), the same version of dictionary datasets will be implemented for conversion from SI to SDTM.

#### **Generation of RTF Files**

RTF files will be generated for all reporting efforts described in the RAP.

#### 11.3.2. Reporting Standards

#### General

The current GSK Integrated Data Standards Library (IDSL) will be applied for reporting, unless otherwise stated (IDSL Standards Location:

https://spope.gsk.com/sites/IDSLLibrary/SitePages/Home.aspx):

- 4.03 to 4.23: General Principles
- 5.01 to 5.08: Principles Related to Data Listings
- 6.01 to 6.11: Principles Related to Summary Tables
- 7.01 to 7.13: Principles Related to Graphics
- Do not include participant level listings in the main body of the GSK Clinical Study Report. All participant level listings should be located in the modular appendices as ICH or non-ICH listings.

#### **Formats**

- All data will be reported according to the actual treatment the participant received unless otherwise stated.
- GSK IDSL Statistical Principles (5.03 & 6.06.3) for decimal places (DP's) will be adopted for reporting of data based on the raw data collected, unless otherwise stated.
- Numeric data will be reported at the precision collected on the eCRF.
- The reported precision from non eCRF sources will follow the IDSL statistical principles but may be adjusted to a clinically interpretable number of DP's.

#### **Planned and Actual Time**

- Reporting for tables, figures, and formal statistical analyses:
  - Planned time relative to dosing will be used in figures, summaries, statistical analyses and calculation of any derived parameters, unless otherwise stated.
  - The impact of any major deviation from the planned assessment times and/or scheduled visit days on the analyses and interpretation of the results will be assessed as appropriate.
- Reporting for Data Listings:
  - Planned and actual time relative to study drug dosing will be shown in listings (Refer to IDSL Statistical Principle 5.05.1).

- Unscheduled or unplanned readings will be presented within the participant's listings.
- Visits outside the protocol defined time-windows (i.e. recorded as protocol deviations) will be included in listings but omitted from figures (mean figures only for PK concentrations), summaries, and statistical analyses (excluding statistical analyses of PK parameters).

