## 8.4. Statistical Analysis / Methods

Details of the planned displays are provided in Appendix 9: List of Data Displays and will be based on GSK Data Standards and statistical principles.

Individual concentration-time profiles will be created for LH, FSH and progesterone. For each parameter, the profiles for both treatments will be overlaid on the same plot.

Actual values for serum LH, FSH, and progesterone levels will be listed and summarized by treatment using descriptive statistics; in addition, the mean value with the SD will be presented in a figure. The maximum LH and FSH concentration of each treatment period will be identified for each subject and listed with treatment and day and summarized by treatment.

For each parameter (LH, FSH, and progesterone), the concentrations will be plotted by treatment and timepoint using box-plots displaying the median, range, 25th and 75th percentiles. Maximum LH and FSH will be plotted within the same figure.

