#### **Unscheduled Visits**

- Unscheduled visits will not be included in summary tables except for determining the worst-case values.
- Unscheduled visits will not be included in figures.
- All unscheduled visits will be included in listings.

Descriptive Summary Statistics					
Continuous Data Refer to IDSL Statistical Principle 6.06.1					
Categorical Data	N, n, frequency, %				
Graphical Displays					
Refer to IDSL Statistical Principals 7.01 to 7.13.					

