No.	Population	IDSL / Example Shell	Title	Programming Notes	Deliverable [Priority]	
C-SSRS	3					
2.19.	Safety	CSSRS4	Listing of C-SSRS Suicidal Ideation and Behavior Data	Only include participants who have suicidal ideation or behavior	SAC	
Liver E	vent					
2.26.	Safety	LIVER1	Summary of Liver Monitoring/Stopping Event Reporting		SAC	
2.27.	Safety	LIVER10	Summary of Hepatobiliary Laboratory Abnormalities		SAC	

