# 11.9.9. Pharmacodynamic Table

Pharma	Pharmacodynamic: Tables							
No.	Population	IDSL / Example Shell	Title	Programming Notes	Deliverable [Priority]			
4.1	PD Concentration	PD_T1	Summary of Serum Luteinizing Hormone, Follicle-Stimulating Hormone, and Progesterone Concentration		SAC			
4.2	PD Concentration	PD_T1	Summary of Maximum Serum Luteinizing Hormone and Follicle-Stimulating Hormone Concentration		SAC			

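### Visits outside the protocol windows have no worst-case exception, so an off-window laboratory or QTc value is left out of the worst-case safety tables although the same unscheduled value would count

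*SAP*

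**What the plan says.** Two neighbouring rules in SAP section 11.3.2 deal with results at irregular times.

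- **Out-of-window visits (Planned and Actual Time).** "Visits outside the protocol defined time-windows (i.e. recorded as protocol deviations) will be included in listings but omitted from figures". The full scope reads "omitted from figures (mean figures only for PK concentrations), summaries, and statistical analyses (excluding statistical analyses of PK parameters". Both parenthetical limits concern PK: for PK concentrations only mean figures are affected, and the statistical analyses of PK parameters are exempt. Safety and worst-case values are not mentioned.
- **Unscheduled visits.** "Unscheduled visits will not be included in summary tables except for determining the worst-case values". They are also kept out of figures and shown in listings.

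Section 11.9.5 lists the worst-case safety displays as summaries, among them "Summary of Clinical Chemistry Results by Maximum Grade Increase Post-Baseline Relative to Baseline" (Table 2.8, with 2.10 for hematology and 2.13 for urinalysis), "Summary of Maximum QTc Values Post-Baseline Relative to Baseline by Category" (Table 2.16, with 2.17 for the maximum increase) and "Summary of Hepatobiliary Laboratory Abnormalities" (Table 2.27).

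On the hormone side, Table 4.1 is "Summary of Serum Luteinizing Hormone, Follicle-Stimulating Hormone, and Progesterone Concentration". Section 8.4 adds a per-period maximum for two hormones: "The maximum LH and FSH concentration of each treatment period will be identified for each subject". No such maximum is defined for progesterone. Its 6.36 nmol/L cut-off serves only to categorise the PK boxplots (sections 7.1.4 and 7.2.4; Figures 3.19 to 3.21).

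**The concern.** A worst-case table should show the most extreme value each participant reached on treatment. For that purpose the exact time of a draw matters little: a high ALT or a long QTc is no less real for having been measured outside its window. The SAP accepts this for unscheduled visits and then gives no such allowance to scheduled visits that ran early or late.

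At stake is whether the worst-case safety tables are complete. Liver safety is an active topic in this plan, since the RAP amendment added liver-event tables, liver-enzyme plots and PK boxplots by ALT category. A severe laboratory grade could be missing from the summary tables and be visible by participant only in listings, which section 11.3.2 keeps out of the main body of the study report.

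**Working it through.** The SAP gives no figure to reproduce. The check compares the rules with the displays and the schedule.

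**1. The two rules compared**

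| | Out-of-window scheduled visit | Unscheduled visit |
|---|---|---|
| Listings | kept | kept |
| By-visit summaries | omitted | omitted |
| Worst-case summaries | omitted (no exception written) | kept (exception written) |
| Figures | omitted, except non-mean PK concentration figures | omitted |

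The rules differ only in the worst-case row. That off-window visits are omitted there is an inference: the word for summaries is unqualified, and the exceptions that were written are for PK only.

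**2. Displays reached.** Tables 2.8, 2.10, 2.13, 2.16, 2.17 and 2.27 are all titled as summaries. So are hormone Tables 4.1 and 4.2. The PD figures (4.1 to 4.3) are reached too, because the figure exception covers PK concentrations only.

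**3. Readings per participant** (Table 2 of the SAP, with the baselines in section 5.2)

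- Laboratory days are -4, 1, 10, 21 and 24. The Treatment A baseline is Day 1 pre-dose, which leaves Day 10, so one off-window draw removes 1 of 1 scheduled post-baseline readings.
- The Treatment B laboratory baseline is Day 10, which leaves Days 21 and 24, so one off-window draw removes 1 of 2.
- ECGs are denser. After coadministration starts there are three on Day 11, three on Day 15, and one each on Days 21 and 24: 3 + 3 + 1 + 1 = 8. One lost reading matters less there.
- Progesterone after coadministration starts is scheduled on Days 21 and 22, so one off-window sample removes 1 of 2.

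**4. Direction for one participant.** The maximum over a subset of readings cannot exceed the maximum over all of them. Omission leaves a participant's own maximum absolute value unchanged or lowers it. For baseline-relative tables this holds only if the baseline is unaffected; dropping an off-window baseline could move the change either way.

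**5. Size for a percentage.** The SAP gives no sample size, so N = 15 to 30 is an assumption. Let k participants have the event.

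- If the omitted participant had the event and drops out of the numerator, the incidence falls by at most 1/N: 1/15 = 6.7 points, 1/30 = 3.3 points.
- If the omitted participant did not have the event and leaves the denominator, the incidence rises by k/(N-1) - k/N = k/[N(N-1)]. With k = 1 and N = 20: 1/19 - 1/20 = 5.26% - 5.00%, about 0.3 points.

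The 3 to 7 points are therefore a conditional maximum, and the sign can reverse.

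**The case against.** The strongest case on the other side is that little would change in practice.

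- **Frequency.** Participants are admitted on Day -4 and discharged on Day 25, so every scheduled on-study draw is made in clinic. The windows are left to the protocol, and nothing in the SAP suggests that many draws will miss them. This stands.
- **Other routes to the tables.** Adverse event tables and the liver monitoring/stopping table (2.26) report events, so a value reported as an event is still tabulated. Listings 22 to 27 show laboratory toxicities. Section 11.3.2 also calls for the impact of major timing deviations to be assessed as appropriate. This stands, but none of it puts the value back into Tables 2.8, 2.10, 2.13, 2.16, 2.17 or 2.27.
- **Intent.** Section 11.4.1 has a row covering any post-baseline visit, and the unscheduled-visit rule shows that worst-case values are meant to be inclusive. A drafting gap is the likelier explanation. A programmer following the text would still filter these values out.

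A reader might infer three stronger things that the SAP does not support:

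- **That the rule can only lower reported toxicity.** This is true of a participant's own maximum absolute value but not of percentages, as step 5 shows.
- **That a high progesterone would be lost from a worst-case count.** No such count or maximum exists for progesterone. The loss is confined to Table 4.1, the PD figures and the 6.36 nmol/L boxplot categories, and Listing 40 lists the serum hormone concentrations. Because unscheduled visits are also kept out of figures, the boxplot question is a separate clarification and not part of the mismatch between the two rules.
- **That an off-window toxicity disappears from the report.** It remains in the listings.

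**Conclusion.** The point holds as a gap between two adjacent rules. An off-window scheduled laboratory or QTc value is left out of six worst-case safety tables that would count the same value from an unscheduled visit. The result rests on reading the omission from summaries literally and on the absence of any non-PK exception.

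The expected effect is small: few visits should be off-window, and the primary PK parameter analysis is expressly exempt. The exposure is greatest for laboratory grades, with one scheduled post-baseline day in Treatment A and two in Treatment B. Under the assumed N of 15 to 30, one missed event could lower an incidence by up to 3.3 to 6.7 points. Omitting a participant without the event would raise it slightly. The change is worth making because a severe value is the one that a worst-case table exists to show.

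**What to change.** Add to SAP section 11.3.2, Planned and Actual Time:

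> *Off-window results are excluded from by-visit summaries and mean figures only. Like unscheduled results, they are included in determining worst-case values (maximum grade, hepatobiliary abnormalities, maximum QTc, and maximum LH and FSH).*

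State separately that off-window progesterone values are kept when assigning subjects to the 6.36 nmol/L categories in Figures 3.19 to 3.21.

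The cost is two sentences and a change to a data filter. No new data are needed and the primary analysis is unaffected. The small downside is that some worst-case values, and some points in individual plots and boxplots, will come from off-nominal times; a footnote can mark them. Table 4.1 would still omit off-window hormone values wherever it is presented by visit, which is reasonable for a by-visit summary.
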